#### Phlebotomy

Novartis	Confidential	Page 20 of 36
SAP Amendment 1		Study No. CICL670F2203

Summary statistics will be provided for duration of exposure, average volume of blood (mL) removed and average frequency of procedure by treatment arm.

For each subject, listing of each phlebotomy administered along with the volume removed and the hematocrit record will be produced. Any subjects from DFX FCT arm with Phlebotomy during post treatment follow up will be flagged.

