4.1 Description of study design

This is a Phase II, multicenter, open-label, randomized two-year study in 150 adults confirmed by HH genotype with iron overload. Eligible patients will be identified during a 4-week screening period, then randomized in a 2:1 ratio (100 patients to deferasirox FCT and 50 patients to phlebotomy), and treated for 24 months (104 weeks). After end of treatment (EOT), there is a standard 30-day safety follow-up. Please refer to Section 7 for screening and assessment details.

An initial dose of deferasirox FCT 7 mg/kg/day will be used for 3 months (12 weeks), then adjusted according to the ferritin level. Dose adjustments based on safety are allowed at any time.

Phlebotomy will be conducted at a frequency determined by the physician.

Both phlebotomy and deferasirox FCT must be interrupted when the study-defined target SF $\leq 100 \ \mu g/L$ is achieved. Deferasirox FCT may be reinitiated when SF $\geq 300 \ \mu g/L$, according to deferasirox label; phlebotomy may be reinitiated when SF $> 100 \ \mu g/L$, based on standard of care practice. Following end of treatment, patients will enter a 30-day safety follow-up period. Concomitant medications and AEs will be collected during this period.

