Patients should not make up missed doses. A missed dose is when the full dose is not taken within 8 hours of the usual time of the daily dose. Omit that day's dose, and resume with the next scheduled dose.

Dose adjustments for safety are allowed at any time and must be in increments or decrements of 3.5 or 7 mg/kg/day. For this study, the maximum dose of deferasirox FCT is 14 mg/kg/day.

Patients randomized to phlebotomy will receive treatment at a frequency determined by the treating physician's judgment for optimal iron control. Phlebotomy must be interrupted when a patient achieves the target SF $\leq 100 \ \mu$ g/L. Treatment may be re-initiated when SF $> 100 \ \mu$ g/L.

Patients randomized to deferasirox FCT are not allowed to receive phlebotomy during the study treatment.

Patients randomized to the deferasirox FCT arm who discontinued from treatment may receive phlebotomy during Post-treatment Ocular Follow-up at a frequency determined by the physician.

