6.4.2 Permitted concomitant therapy requiring caution and/or action

Concomitant administration of deferasirox and vitamin C has not been formally studied. Vitamin C up to 200 mg/day has not been associated with adverse consequences.

Caution must be exercised if taking deferasirox in combination with the following:

- Drugs with a known ulcerogenic potential, such as NSAIDs, corticosteroids, oral bisphosphonates, or anticoagulants which may increase the risk of gastrointestinal irritation and bleeding
- Deferasirox is a weak CYP3A4 inducer and may potentially decrease serum levels of substances metabolized through CYP3A4
- Deferasirox is a moderate inhibitor of CYP2C8 and may increase serum levels of substances metabolized through CYP2C8 (e.g. repaglinide, paclitaxel).
- Deferasirox can potentially increase the levels of substances metabolized through CYP1A2 (e.g. theophylline, clozapine, tizanidine). Monitor theophylline levels and consider theophylline dose reduction.

• Potent UGT inducers (e.g. rifampicin, phenytoin, phenobarbital, ritonavir) may decrease deferasirox concentration.

6.4.3 **Prohibited concomitant therapy**

- Aluminium-containing antacid therapies may bind to deferasirox.
- Bile acid sequestrants (e.g., cholestyramine, colesevelam, colestipol) decrease deferasirox systemic exposure.
- Other iron chelators (deferoxamine, deferiprone, deferasirox) during study treatment and Post-treatment Ocular Follow-up phases
- Any investigational drug other than study medication

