7.1 Study flow and visit schedule

Table 7-1 lists all assessments and indicates with an "X" the visits when they are performed. All data obtained from these assessments must be supported in the patient's source documentation.

Scheduled assessments should be done on the designated day, or as close to it as possible, i.e., not exceeding ± 3 days for assessments scheduled at Week 2 and Week 4, not exceeding ± 7 days for monthly visits until Week 104 (End of Treatment Visit), and not exceeding ± 30 days for assessments done approximately every 6 months, such as ocular and ECG assessments. In this clinical trial, a week is 7 calendar days, and 1 month is 30 days.

FRANCE SPECIFIC ONLY: The additional assessments of creatinine and creatinine clearance at Week 1 and Week 3 after start of treatment, and weekly checks of creatinine and creatinine clearance during the first month of dose increases, are specific to patients enrolled in sites from France. These assessments are NOT included in the Table 7-1, and should be recorded as unscheduled visits.

No eCRF will be used as a source document.

	Category	Protocol Section	Screening		Randomization								Treatment Period					End of study treatment (EoT)	30-day Follow up	Post-treatment Follow-up *
Weeks			-4	-2	Day 1	2	4	8	12	16	20	24	28, 32, 36, 40, 44, 48	52	56, 60, 64, 68, 72	76	80, 84, 88, 92, 96, 100	104	108	
Informed Consent	D	7.1.2	Х																	
IRT Registration	S	7.1.2.1	Х																	
Demography	D	7.1.2.3	Х																	
Inclusion/ exclusion	D	7.1.2	Х	Х																
HH history	D	7.1.2	х																	
Medical History	D	7.1.2.3	Х																	
Prior and concomitant medication / procedures	D	6.4	Con	tinuou	ısly till 30	day	s aft	er las	st dos	se of	study	treatr	nent							
Ocular History	D	7.1.2.3	Х																	

Table 7-1 Visit evaluation schedule

Novartis Amended Protocol Version 01 (Clean)

	Category	Protocol Section	Screening		Randomization								Treatment Period					End of study treatment (EoT)	30-day Follow up	Post-treatment Follow-up *
Weeks			-4	-2	Day 1	2	4	8	12	16	20	24	28, 32, 36, 40, 44, 48	52	56, 60, 64, 68, 72	76	80, 84, 88, 92, 96, 100	104	108	
Cirrhosis History	D	7.1.2	Х																	
Randomization	D	6.5			х															
Disposition	D	7.1.2		X														Х		Х
Molecular Testing of HH	D	7.2.2.6.1	X																	
Physical examination	S	7.2.2.1	Х		x	х	Х	х	Х	Х	х	Х	x	х	Х	Х	Х	Х		
Vital signs	D	7.2.2.2	Х		Х	Х	Х	Х	Х	Х	х	Х	Х	Х	Х	х	х	Х		

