Height	D	7.2.2.3	Х																	
Weight	D	7.2.2.3	Х		Х	Х	Х	Х	Х	Х	х	Х	Х	Х	х	х	х	Х		
Best Corrected Visual Acuity	D	7.2.2.5	Х									Х		Х		Х		х		Х

Confidential

Page 44 Protocol No. CICL670F2203

	Category	Protocol Section	Screening		Randomization								Treatment Period					End of study treatment (EoT)	30-day Follow up	Post-treatment Follow-up *
Weeks			-4	-2	Day 1	2	4	8	12	16	20	24	28, 32, 36, 40, 44, 48	52	56, 60, 64, 68, 72	76	80, 84, 88, 92, 96, 100	104	108	
Slit Lamp Exam (w/ LOCS III)	D	7.2.2.5	Х									Х		Х		х		Х		х
Tonometry	D	7.2.2.5	Х									Х		Х		х		Х		х
Fundus Photography	D	7.2.2.5	Х									Х		х		х		Х		х
ECG	D	7.2.2.7.1	Х									Х		Х		Х		Х		
Audiometry	D	7.2.2.4	х									х		х		Х		Х		
Cirrhosis assessment	D	7.2.2.8	Х																	
Hematology	D	7.2.2.6.2	х	Х	х	Х	х	Х	Х	Х	Х	Х	х	х	Х	Х	х	Х		
Chemistry	D	7.2.2.6.3	Х	Х	Х	Х	Х	Х	Х	Х	Х	Х	х	Х	Х	Х	X	Х		
Coagulation	D	7.2.2.6.6	х	х	х	х	х	Х	Х	Х	х	х	х	Х	Х	Х	x	Х		
Urinalysis	D	7.2.2.6.4	х	х	Х	Х	Х	Х	Х	Х	Х	х	х	Х	Х	Х	X	Х		

Confidential

Page 45 Protocol No. CICL670F2203

	Category	Protocol Section	Screening		Randomization								Treatment Period					End of study treatment (EoT)	30-day Follow up	Post-treatment Follow-up *
Weeks			-4	-2	Day 1	2	4	8	12	16	20	24	28, 32, 36, 40, 44, 48	52	56, 60, 64, 68, 72	76	80, 84, 88, 92, 96, 100	104	108	
Urine protein/creatinine ratio	D	7.2.2.6.4	Х	X	X	X	Х	Х	Х	Х	Х	Х	х	Х	X	Х	X	X		
Transferrin saturation	D	7.2.2.6.7	Х	Х	X	Х	Х	X	Х	Х	Х	Х	X	Х	X	X	X	X		
Hepatitis tests	D	7.2.2.6.5	X																	
Serum Ferritin	D	7.2.1.1	Х	X	X	Х	Х	X	X	Х	Х	X	x	X	X	X	X	Х		
Serum Pregnancy	D	7.2.2.6.8	X																	
Urine Pregnancy	D	7.2.2.6.8			Х													Х		
Phlebotomy record	D	6.6.3.3	Con	itinuol	usly from	6 mc	onthe	3 bef	ore R	ando	mizat	tion to	End of study f	treatm	ent.					
Drug dispensing	S	6.6			X		Х	Х	X	Х	Х	X	x	х	Х	Х	X	Х		
Study Drug administration	D	6.6			Daily in	take	of st	tudy	drug											

Confidential

Page 46 Protocol No. CICL670F2203

		r	1		1														1	
	Category	Protocol Section	Screening		Randomization								Treatment Period					End of study treatment (EoT)	30-day Follow up	Post-treatment Follow-up *
Weeks			-4	-2	Day 1	2	4	8	12	16	20	24	28, 32, 36, 40, 44, 48	52	56, 60, 64, 68, 72	76	80, 84, 88, 92, 96, 100	104	108	
Adverse events	D	8.1	Con	tinuou	isly after	ICF	signa	ature	and	till 30	days	after	last dose of st	tudy tre	eatment					

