#### Date of First/Last Administration of Study Treatment

For Deferasirox FCT:

- The date of first administration of study treatment is derived as the first date when a non-zero actual dose of study treatment was administered as recorded on Dose Administration Record (ZQ) Electronic Case Report Form (eCRF).
- The date of last administration of study treatment is defined as the last date when a nonzero actual dose of study treatment was administered as recorded on ZQ eCRF.

For Phlebotomy:

- The date of first administration of study treatment is derived as the first date when a non-zero volume of blood removed was recorded on Phlebotomy Record eCRF (FAZU) on or after the randomization date.
- The date of last administration of study treatment is defined as the last date when a nonzero volume removed of blood was recorded on Phlebotomy Record eCRF (FAZU). This date will also be referred as 'last date of study treatment'.

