#### 2.5.2 Statistical Hypothesis, Model, and Method of Analysis

To characterize long-term ocular safety, the incidence of treatment-emergent ocular AEs (new or worsening from baseline) will be summarized (along with two-sided exact binomial 95% CIs [Clopper and Pearson, 1934]) by preferred term, overall and by severity, type of AE (e.g. serious, leading to study drug discontinuation, requiring dose adjustment or/and interruption), and relation to study treatment.

Treatment-emergent AEs are defined as AEs started during on-treatment period: from the day of the first dose of study medication or the first phlebotomy to 30 days after the last dose of study medication or last phlebotomy.

All ocular AEs included under "Lens disorders, retinal disorders and optic neuritis" Adverse Event of Special Interest (AESI, listed in the compound case retrieval strategy) will be reported.

Novartis	Confidential	Page 22 of 36
SAP Amendment 1		Study No. CICL670F2203

The above analysis will also be repeated for the overall period (on-treatment & post-treatment).

The analyses will be descriptive. No formal hypothesis testing is planned for this key secondary objective.

A listing of Ocular AEs will also be generated, and post-treatment events will be flagged.

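### The documents conflict on what is recorded in Post-treatment Ocular Follow-up: the schedule gives the SAP's crossover flag and between-exam ocular AEs no data source, and the last phlebotomy has no end-of-treatment limit

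*SAP*

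**What the plan says.** **What may happen in the phase.** Under Protocol 6.1.1, patients who stop deferasirox "may receive phlebotomy during Post-treatment Ocular Follow-up at a frequency determined by the physician". Protocol 6.4.3 prohibits "Other iron chelators (deferoxamine, deferiprone, deferasirox) during study treatment and Post-treatment Ocular Follow-up phases". Protocol 4.3 runs the phase up to Month 24.

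**What the schedule collects.** In Protocol Table 7-1, the row "Phlebotomy record" runs from 6 months before randomization to end of study treatment. The row "Prior and concomitant medication / procedures" and the adverse event row stop 30 days after the last dose. Protocol 4.1 agrees, saying of the 30-day safety follow-up that "Concomitant medications and AEs will be collected during this period". The post-treatment column is marked only for disposition and the four eye assessments. Protocol 6.6.3.3 asks for phlebotomy details only for patients randomized to phlebotomy.

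**What the SAP plans to use.** SAP 2.3.1 says "Any subjects from DFX FCT arm with Phlebotomy during post treatment follow up will be flagged". SAP 2.5.2, on treatment-emergent ocular AEs, adds "The above analysis will also be repeated for the overall period (on-treatment & post-treatment"). SAP 2.1.1 starts the post-treatment period on day 31 after the last administration. It dates the last phlebotomy as the "last date when a nonzero volume removed of blood was recorded on Phlebotomy Record eCRF (FAZU").

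**The concern.** Ocular safety is the key secondary objective and the subject of the post-marketing requirement, and the post-treatment phase exists to keep eye data coming from patients who stop early. The SAP reports on phlebotomy and ocular AEs in that phase, but the visit schedule does not collect them there.

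Three things are at stake. An empty crossover flag could be read as no crossover when it means no record. The overall-period ocular AE incidence could be understated, because events between exams have no scheduled route into the database. And if sites do record follow-up bleeds, an open-ended definition of the last phlebotomy can turn post-treatment time into on-treatment time for one arm and not the other.

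**Working it through.** The plan states no figure on this point that could be reproduced, so the check sets the texts side by side and then sizes the gap.

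**1. Planned use against scheduled source, after the 30-day follow-up**

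| Planned use | Scheduled source in Table 7-1 | Other route |
|---|---|---|
| Flag for phlebotomy in the deferasirox arm (SAP 2.3.1) | None; the record ends at end of study treatment | Protocol 6.4.1, but on the concomitant medication or procedures page, not the Phlebotomy Record |
| Check on prohibited chelators (Protocol 6.4.3) | None; the row ends 30 days after last dose | Protocol 6.4.1 |
| Overall-period ocular AEs (SAP 2.5.2) | None; the row ends 30 days after last dose | Findings at the exam that meet the AE definition (Protocol 7.2.2.5); SAEs suspected to be related (Protocol 8.2.2) |
| Overall-period examination tables (SAP 2.6.2) | Eye exams are scheduled in the post-treatment column | Not needed |

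The SAP's post-treatment period begins on day 31, the point at which scheduled AE and medication recording has just ended. The first three rows therefore have no scheduled source in that period. The fourth does.

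**2. Length of the uncovered interval**

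Phlebotomy: (104 − stop week) × 7 days. Medication and AEs: the same, less 30 days.

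| Stop week | Phlebotomy record | Medication and AE record |
|---|---|---|
| 24 | 80 × 7 = 560 days | 560 − 30 = 530 days |
| 52 | 52 × 7 = 364 days | 364 − 30 = 334 days |
| 76 | 28 × 7 = 196 days | 196 − 30 = 166 days |

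For the week-24 stop, 530/560 is about 95% of the remaining time.

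**3. How many deferasirox patients**

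Protocol 10.8 gives 24% dropout by month 6 in the earlier study of the dispersible tablet and expects at least 60 of 100 followed for 24 months. Entry to the phase needs at least 6 months of assessments (Protocol 4.1.1). Assume 24 are lost by month 6 and exactly 60 are still on treatment at month 24:

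- 100 − 24 = 76 on treatment at month 6.
- 76 − 60 = 16 stop later and could enter.

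Each contributes 1 to 3 later scheduled exams (weeks 52, 76 and 104, depending on when they stop). If all 16 join, that is 16 to 48 exams. If half join, 8 patients give 8 to 24.

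The count depends on the assumptions. With L patients lost by month 6 and 60 on treatment at the end, it is 40 − L, so it rises if early dropout is lower than 24. The 60 in Protocol 10.8 are described as followed, not as on treatment. If some of them were in ocular follow-up, more than 16 would have stopped treatment after month 6.

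**4. The last-phlebotomy rule**

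SAP 2.1.1 bounds the first phlebotomy (on or after randomization) but sets no end-of-treatment bound on the last. Deferasirox dates come from the dose administration page, so follow-up bleeds cannot move them. In the phlebotomy arm, patients who stop study treatment go on to standard of care (Protocol 4.3), which is phlebotomy (Protocol 1.1 and 2.5). If those bleeds are entered on the Phlebotomy Record, the on-treatment window (SAP 2.1.1), exposure duration (SAP 2.3.1) and treatment-emergent AE window (SAP 2.5.2) all extend to 30 days after the latest bleed. For a patient who stops at week 24 and is bled at week 104, the shift is 560 days. A longer window can only add subjects with an event to that arm's treatment-emergent incidence.

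**The case against.** The best counter-argument is Protocol 6.4.1. It requires all medications and significant non-drug therapies given during the study to be entered, with no 30-day limit. Patients who discontinue treatment are not treated as withdrawn (Protocol 7.1.5), and end of study includes the ocular follow-up (Protocol 4.3). SAP 2.3.2 plans to list and flag therapies that start more than 30 days after the last treatment, so the SAP expects late records. Protocol 7.2.2.5 also mentions post-treatment follow-up eCRFs whose content is not shown. This stands: a reader might infer that the data are absent, and the documents do not prove that. What they show is a conflict, and sites may follow either text.

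A reader might also infer that the overall-period ocular analyses cannot be run. That goes too far. SAP 2.6.2 analyses examinations by eye side, arm and time point, without phlebotomy or chelator data as inputs, and plans swimmer plots that separate on-treatment from post-treatment exams. Only the reading of post-treatment findings by later treatment suffers.

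On AEs, Protocol 8.1.1 sets 30 days as a minimum. Exam findings that meet the AE definition are recorded with no stated time limit, and lens and retinal disorders are what those exams are built to detect. The gap is therefore confined to events arising between exams. Nothing in the documents supports a forecast that the post-treatment table would be nearly empty.

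Finally, the two faults exclude each other for any one record: if the schedule is followed, no follow-up bleed is entered and the window cannot stretch. That is true, but each reading still leaves one fault in place.

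**Conclusion.** The point holds as an unresolved conflict between Table 7-1 and Protocol 6.6.3.3 on one side and Protocol 6.4.1 and the SAP on the other. If the schedule is followed, the crossover flag and the chelator check have no scheduled source. Between-exam ocular AEs are then not systematically collected, and the overall-period ocular AE incidence may be understated by an amount the documents cannot fix. If follow-up bleeds are entered instead, on-treatment time can lengthen in the phlebotomy arm only.

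The uncovered interval is longest for a week-24 stop. About 16 deferasirox patients are exposed to the gap under the two stated assumptions, fewer if not all join the phase. A larger figure, with every discontinuing patient contributing three later exams, might be inferred. It would require all of them to stop at month 6, which the documents do not suggest.

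The primary endpoint does not depend on any of this. The on-treatment ocular AE analysis is touched only through the last-phlebotomy rule. The matter should be corrected, but it does not undermine the trial.

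**What to change.** 1. **Protocol Table 7-1 and 6.6.3.3.** Reconcile them with 6.4.1 and the SAP. Extend three items to the last ocular follow-up visit: the phlebotomy record (both arms), iron-chelator and eye-related therapy, and ocular AEs. Collect them at the existing six-monthly exams and at the reminder call already made one month before each exam. No treatment rule changes.
2. **SAP 2.1.1.** Define the last phlebotomy as the last non-zero removal on or before the end-of-treatment date, so that later bleeds feed the crossover listing without lengthening the on-treatment period.
3. **Follow-up already completed.** SAP section 4 describes visit delays in the past tense, so conduct was advanced when Amendment 1 was written, and reopening pages cannot recover earlier follow-up prospectively. For those patients, state in the SAP and the study report that an empty flag does not mean no crossover and that the post-treatment ocular AE count is incomplete.

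The cost is a minor amendment, some eCRF pages opened at visits already planned, a few SAP sentences and a little more site data entry. Items 2 and 3 remain possible even if item 1 comes too late.

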#### **2.3.2 Prior and Concomitant Therapies**

#### **Concomitant Medications**

Concomitant therapy is defined as all interventions (therapeutic treatments and procedures) other than the study treatment administered to a subject coinciding with the study treatment period. Concomitant therapy includes medications (other than study treatments) starting on or after the start date of study treatment or medications starting prior to the start date of study treatment and continuing after the start date of study treatment.

Concomitant medications will be coded using the World Health Organization (WHO) Drug Reference Listing (DRL) dictionary that employs the WHO Anatomical Therapeutic Chemical (ATC) classification system and summarized by ATC level 2 and preferred term using frequency counts and percentages. Surgical and medical procedures will be coded using MedDRA and summarized by SOC and preferred term. These summaries will include:

- 1. Medications starting on or after the start of study treatment but no later than 30 days after start of last dose of study treatment and
- 2. Medications starting prior to start of study treatment and continuing after the start of study treatment.

All concomitant therapies will be listed. Any concomitant therapies starting and ending prior to the start of study treatment or starting more than 30 days after the last date of study treatment will be flagged in the listing. The safety set will be used for all concomitant medication tables and listings.

#### **Prior Therapies**

Prior medication is defined to be drugs starting and ending prior to the first dose of study medication. The number and percentage of subjects who received any prior medications will be listed and summarized by treatment arm by lowest ATC class, preferred term, and treatment.

The above analyses will be performed using the FAS.

# 2.4 Analysis of the Supporting Primary Objective

The primary objective of this study is to assess the response rate (RR) of deferasirox FCT and phlebotomy treatment arms where response is defined by achieving target Serum Ferritin (SF)  $\leq 100 \ \mu g/L$  on or before month 24 (week 104).

#### 2.4.1 Primary Endpoint

The primary endpoint is the RR by month 24 (week 104), i.e. the proportion of subjects whose SF  $\leq$  100 µg/L for the first time on or before month 24 (week 104). All post-baseline SF values collected until week 104 (EOT) will be considered to derive the primary endpoint (including unscheduled and repeat measurements).

The primary analysis will be carried out in the FAS.

#### 2.4.2 Statistical Hypothesis, Model, and Method of Analysis

RR is defined as the proportion of subjects whose  $SF \le 100 \ \mu g/L$  at any time on or before month 24 and the response rate will be summarized (proportion) by treatment arm along with two-sided exact binomial 95% CIs [Clopper and Pearson 1934]. The analyses will be descriptive only. No formal hypothesis testing is planned.

In addition, a box plot for serum ferritin by timepoint and treatment arm and line graph for individual subject values for serum ferritin by timepoint and treatment arm will be plotted.

